4.9.2.1. Gated Secondary Efficacy Analyses

Bretz’s graphical approach will be utilized to provide strong control of the study-wise Type I error rate for the primary and secondary clinical efficacy hypotheses at alpha level of 0.05 (Bretz et al. 2009, 2011) in the moderate tau population. The statistical significance, outlined using alpha levels in a frequentist testing paradigm, will be determined based on the following multiplicity graph of hypotheses regarding the LY3372689 slowing the cognitive and/or functional decline and tau SUVR level of AD with demonstrated presence of moderate levels of tau pathology (the blue ovals represent the high dose arm and the orange ovals represent the low dose arm):

The Bayesian DPM will be used to analyze the primary endpoint of iADRS, the NCS2 model will be utilized for secondary clinical efficacy endpoints including CDR-SB, iADL, ADAS-Cog13, and MMRM will be used to analyze the tau imaging biomarker endpoint AD-signature VOI using CereCrus as the reference region for brain tau deposition as measured by flortaucipir F18 PET standard uptake value ratio (SUVR) value.

The frequentist analyses for the clinical endpoints will utilize the endpoint averaging across Week 64, Week 76, and Week 88. The tau imaging biomarker endpoint will be analyzed based on the LS mean change from the baseline at Week 76.

As mentioned in Section 2, additional CSFs for iADRS using Bayesian DPM will be established to control the Type I error at two-sided 0.05 level in the graphical testing scheme (Section 4.9.2.1). To test the hypothesis of a disease progression benefit as measured by iADRS using the Bayesian DPM, the posterior probability of superiority in cognitive/functional slowing for each active treatment arm will be calculated. The superiority is defined by $\Pr(\text{DPR} < 0.75) > X$, where the value of X is determined via simulation to control the test at the corresponding alpha level. If the posterior probability is above the threshold for at least one active treatment arm (which controls the overall false positive rate at approximately 2.5% one-sided), then a statistical significance claim of cognitive/functional slowing will be made. Success will be declared at a graphical node if the posterior probability of at least 25% slowing of disease progression as measured by the iADRS in high dose and the low dose is greater than a certain threshold:

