- Probability (at least 25 % slowing of disease progression on iADRS in LY3372689 high dose relative to placebo) > probability threshold 1.
- Probability (at least 25 % slowing of disease progression on iADRS LY3372689 low dose relative to placebo) > probability threshold 2.

These two thresholds will be calculated after unblinding at PODBL to establish the accurate probability thresholds that correspond to each alpha level as shown in graphical testing scheme above. As the thresholds can be sensitive to the underlying assumptions of placebo trajectory and the variance-covariance matrix, the methodological approach to find the probability thresholds is pre-specified below. The established thresholds will be documented in the CSR.

1. The NCS2 results for the iADRS (Section 4.8.2.1) from the moderate tau population will provide the underlying assumptions that are needed for this simulation. The following will be utilized: the LS mean placebo trajectory and the number of participants with data from the placebo arm at each visit; the pooled variance covariance matrix as estimated from the NCS2.
2. To create a null distribution, simulate multivariate normal data for the number of participants from the moderate tau population representing the placebo arm, assuming all participants have the same decline as the placebo arm from the NCS model and the same variability. The amount of data simulated for each treatment arm will reflect the exact number of participants at each visit from the placebo arm.
3. The posterior probability of at least 25% slowing is calculated by fitting the Bayesian DPM to each 100,000 simulated dataset. The Bayesian DPM as described in Section 4.8.1 but without covariate adjustment. The threshold is the lowest value at which at least $(\alpha/2 \times 100)\%$ of the simulated posterior probabilities are larger. Note that the probability threshold 2 will be re-calculated if it makes all the way down to tau imaging biomarker in the high dose arm.

The tests for the rest of the graph: CDR-SB, iADL, and ADAS-Cog13 will be based on the p-value of the difference of averaged LSM change across Week 64 to Week 88 between the treatment arms; tau imaging biomarker endpoint AD-signature VOI will be based on the p-value of the difference of LSM change at Week 76 between the treatment arms.

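### SAP 4.9.2.1, step 3: the rule for the iADRS thresholds in the graphical testing scheme is worded the wrong way round and, taken literally, returns 0

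*SAP*

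**What the plan says.** SAP Section 4.9.2.1 tests iADRS in the moderate tau population with the Bayesian disease progression model (DPM), one node per dose. A node succeeds if the posterior probability that the disease progression ratio (DPR) is below 0.75, i.e. at least 25% slowing, is above a cut-off X, "where the value of X is determined via simulation to control the test at the corresponding alpha level". For the high dose the condition reads "slowing of disease progression on iADRS in LY3372689 high dose relative to placebo) > probability threshold 1"; the low dose has its own threshold 2. The stated purpose is "to control the Type I error at two-sided 0.05 level in the graphical testing scheme", and success in at least one arm is described as a rule "which controls the overall false positive rate at approximately 2.5% one-sided".

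No numerical thresholds are given. They are to be worked out after unblinding. Null trials are simulated in which every arm declines like placebo, posterior probabilities are obtained by "fitting the Bayesian DPM to each 100,000 simulated dataset", and step 3 then converts them into a cut-off: "The threshold is the lowest value at which at least" (α/2 × 100)% "of the simulated posterior probabilities are larger". Step 3 also provides for threshold 2 to be re-calculated if testing in the high-dose arm succeeds all the way to the tau imaging node.

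SAP Section 2 contains a different rule. If the posterior probability of at least 25% slowing exceeds 0.6 for at least one dose, the trial has met its primary endpoint. The graph thresholds are described as additional to that criterion. Section 2 also says that the method for finding them is fixed before unblinding and that the values will be reported in the CSR.

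**The concern.** In step 3, *lowest* and *at least* pull in opposite directions. A rule that protects the Type I error must make the cut-off high enough that few null trials exceed it. The sentence instead asks for a cut-off low enough that at least a given share exceed it, and then takes the lowest such value.

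This matters more than an ordinary slip because the sentence is the only step that turns the simulated null distribution into thresholds 1 and 2. According to the SAP version history, version 4 removed the pre-specified numerical thresholds of the graph and put the method in their place. Since the numbers are produced after unblinding, the value of pre-specification rests on the recipe giving the right answer mechanically. The same sentence governs the re-calculated threshold 2 and, through the graph, the alpha released to later hypotheses.

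**Working it through.** **1. The argument, which needs no assumed figures.** Let f(t) be the share of the simulated null posterior probabilities (PP) that are larger than t. As t rises, f(t) stays level or falls.

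- As written: min{t : f(t) ≥ α/2}. At t = 0 all continuous PPs are larger, so f(0) = 1 ≥ α/2 and 0 qualifies. No probability is lower, so the threshold is 0.
- As intended: min{t : f(t) ≤ α/2}. This is the empirical (1 − α/2) quantile.
- The other natural repair, max{t : f(t) ≥ α/2}, lands on the same quantile.

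**2. The plan's own figure.** Protocol Section 9.2 and SAP Section 5 state a false-positive rate of about 2.4% for the efficacy criterion. Its inputs are redacted, so it cannot be reproduced independently. A cut-off of 0 could not produce it. If the criterion is PP > 0.6, then under the approximation in step 3 below, 2.4% corresponds to a standard error (SE) of log(DPR) of about 0.196 per arm, or 0.162 for at least one arm.

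**3. Numerical illustration.** Inputs:

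- From the SAP: 100,000 null trials; the DPR < 0.75 target; pass if PP > threshold; prior N(0, 0.25) on log(DPR) (Section 4.8.1), with 0.25 taken as a variance.
- Assumed: the SE of log(DPR), s, from 0.10 to 0.30; node alphas of 0.05, 0.04, 0.025 and 0.01, because the graph is a figure not shown; correlation 0.5 between arms from the shared placebo group.

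Normal approximation, with estimate θ̂ drawn around 0 (true DPR = 1):

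m = θ̂ × 0.25/(0.25 + s²); v = 0.25 s²/(0.25 + s²); PP = Φ((ln 0.75 − m)/√v).

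Example at s = 0.20, α = 0.05. The lower 2.5% point of θ̂ is −1.96 × 0.20 = −0.392. Then m = −0.392 × 0.25/0.29 = −0.338, √v = √(0.25 × 0.04/0.29) = 0.186, and PP = Φ((−0.288 + 0.338)/0.186) = Φ(0.27) ≈ 0.61. The simulated quantile was 0.602, so the two agree apart from Monte Carlo error. In that simulation f(0) = 100%, f(0.6020) = 2.500% and f(0.6021) = 2.498%. Every value from 0 to about 0.602 satisfies the wording, and the wording picks 0.

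| s | Threshold as written | Null pass rate, continuous posterior | Null pass rate, 10,000 posterior draws | Corrected threshold, α = 0.05 (rate per arm) | Corrected threshold, α = 0.025 (rate per arm) |
|---|---|---|---|---|---|
| 0.10 | 0 | 100% | 81.5% | 0.153 (2.50%) | 0.228 (1.25%) |
| 0.13 | 0 | 100% | 94.0% | 0.344 (2.50%) | 0.449 (1.25%) |
| 0.15 | 0 | 100% | 96.8% | 0.445 (2.50%) | 0.553 (1.25%) |
| 0.20 | 0 | 100% | 99.1% | 0.602 (2.50%) | 0.699 (1.25%) |
| 0.30 | 0 | 100% | 99.9% | 0.709 (2.50%) | 0.786 (1.25%) |

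The threshold as written was 0 at all four alphas. The fourth column differs from 100% because a finite set of posterior draws can give a PP of exactly 0, which does not exceed 0; the figure of 10,000 draws is an assumption. If candidate thresholds are restricted to the simulated values, the rule returns their minimum (7.4 × 10⁻¹⁴ to 2.7 × 10⁻⁷), and 99.999% of null trials pass. An arm that truly progresses faster than placebo (DPR = 1.2) also passes a threshold of 0 every time with a continuous posterior.

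A small direct fit of a random-intercept DPM with assumed variances (250 null trials each at 60 and 80 per arm) gave PPs above 0 in every trial.

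**The case against.** The strongest reply is that nobody would use a threshold of 0. Section 4.9.2.1 says that X "is determined via simulation to control the test at the corresponding alpha level" and gives the overall rate it is meant to achieve. Simulating 100,000 null datasets would be pointless if the answer were always 0. Read with its purpose, step 3 has one workable meaning, and both natural repairs give the same cut-off to within the grid used (0.6020 against 0.6021 at s = 0.20). The thresholds must also appear in the CSR, so a zero would be seen. All of this stands.

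Four stronger readings are tempting, and the documents do not support them.

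- *The trial has no valid rule for its primary endpoint.* SAP Section 2 fixes PP > 0.6 for that purpose, and step 3 plays no part in it.
- *The plan abandons Type I control.* The surrounding text requires control. The recipe contradicts that requirement and does not withdraw it.
- *Analysts can choose the rule after seeing the data.* Given the required alpha, the wording leaves almost no room for choice. Calculation after unblinding is disclosed and justified in the SAP as a response to sensitivity to the placebo trajectory and covariance.
- *Every node in the graph would pass.* For the iADRS nodes this is exact only with a continuous posterior. CDR-SB, iADL, ADAS-Cog13 and tau PET still need their own p-values.

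What the reply does not remove is that the operative sentence has to be overridden by its stated purpose before it can be used, at a time when the data are unblinded.

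**Conclusion.** The sentence is wrong as written. Followed literally, it gives a threshold of 0, or the smallest simulated value. In the illustration, 100% of null trials then pass with a continuous posterior, 99.999% if only simulated values are candidates, and 81.5% to 99.9% with 10,000 posterior draws. The plan states about 2.5% one-sided. The zero follows from monotonicity alone. The finite-draw range and the corrected thresholds in the table rest on assumed SEs, the variance reading of the prior and a normal approximation, and should not be taken as the trial's actual cut-offs.

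The reach is limited to probability thresholds 1 and 2, the re-calculated threshold 2, and the alpha those nodes pass on. This is a drafting error whose intent can be recovered. It needs correcting because no numerical graph threshold remains in the SAP to fall back on.

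**What to change.** Replace the sentence in step 3 with: *The threshold is the smallest value exceeded by at most (α/2 × 100)% of the simulated posterior probabilities, i.e. their empirical (1 − α/2) quantile.* Keep success as a posterior probability strictly above the threshold. The same sentence then serves the re-calculation of threshold 2.

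If the thresholds have already been calculated, state in the CSR which rule the code applied.

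The cost is one sentence in the SAP and, if needed, one in the CSR. Design, data collection, sample size and model are unchanged.

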4.9.3. Other Secondary Endpoints Analyses

4.9.3.1. Analysis of Volumetric MRI

Analyses of the following volumetric MRI (vMRI) parameters will be conducted (right + left for all but whole brain volume and ventricular volume):

- Hippocampal volume (mm³)
- Atrophy of total whole brain volume (cm³)
- Enlargement of Ventricular volume (cm³)

To evaluate the changes in vMRI parameters, an MMRM model will be used to compare change from baseline to Week 76 between the treatment arms in the Efficacy Evaluable analysis set within moderate tau population and full study population, respectively.

The change from baseline at each post-baseline visit up to Week 76 will be the dependent variable. The model will include the fixed effects of treatment, visit as a categorical variable, treatment-by-visit interaction, and adjusted for baseline vMRI value and age at baseline. Baseline tau PET category will also be included as a fixed effect to the model when analyzing full study population. The null hypothesis is that the difference in LS mean between both the active treatment arm and placebo equal zero. Analyses including post-Week 76 visits may be included for exploratory purpose.

To assess the relationship of vMRI with efficacy endpoints up to Week 76, Spearman's rank correlation coefficient may be obtained on baseline and change from baseline on vMRI parameters versus change from baseline for iADRS, CDSR-SB, ADAS-Cog13, ADCS-ADL, and MMSE. This will be performed using participants who have both the clinical outcome and vMRI result at Week 52 and Week 76, respectively. This analysis may be performed in moderate tau subpopulation and/or the full study population. The correlation analysis including post-Week 76 timepoints such as Week 100 and Week 124 may be conducted for exploratory purpose.

4.9.3.2. Analysis of Flortaucipir PET Scan

To evaluate the change from baseline in tau imaging parameters, ANCOVA will be used to compare change from baseline in SUVR at Week 76 in the Efficacy Evaluable analysis set. The tau SUVR values from the 4 composite regions: frontal, parietal, lateral occipital, lateral temporal will be evaluated with CereCrus (cerebellar crusteneous) as the reference region. In addition, AD-signature volume of interest (VOI) using CereCrus as the reference region will be evaluated. AD-signature VOI was also known as multi-block barycentric discriminant analysis, MUBADA (Kotari et al., 2023, Shcherbinin et al., 2023).

The tolerance window to remap the tau PET scan to the nearest scheduled scan is +/- 28 days. This remapping rule will be implemented to scans that are taken as the ET visit Flortaucipir F18 PET scan when applicable.

The change from baseline on the tau imaging parameters will be the dependent variable. The ANCOVA model will be adjusted by baseline SUVR value and age at baseline. Baseline tau PET category will be included as a fixed effect to the model applied to full study population. The null hypothesis is that the difference in LS mean change between both the active treatment arm and placebo equals zero. MMRM analysis incorporating tau PET scans at post-Week 76 timepoints may be included for exploratory purpose.

To assess the relationship of tau PET imaging biomarkers with efficacy endpoints at Week 76, Spearman's rank correlation coefficient may be obtained on baseline and change from baseline to Week 76 for the SUVR versus the change from baseline to Week 76 for iADRS, CDR-SB, ADAS-Cog₁₃, ADCS-ADL, and MMSE. This will be conducted using participants who have both the clinical outcome and SUVR result at Week 76, and will be analyzed by treatment group as well as pooling all treatment groups. This analysis may be performed in moderate tau subpopulation and/or the full study population. This correlation analysis including post-Week 76 timepoints may be conducted for exploratory purpose.

4.9.4. Pharmacokinetic Analyses

LY3372689 plasma concentrations will be illustrated graphically and summarized descriptively.

If warranted and based on availability of data, the exposure-response relationship of LY3372689 concentrations to biomarkers, pharmacodynamic endpoints, efficacy endpoints, and/or safety endpoints may be explored. Data from other clinical studies evaluating LY3372689 may be combined with data from this study to support exposure-response analyses. Such analyses may be reported separately.

4.10. Safety Analyses

All safety analyses will group subjects based on the actual treatment received. If a patient receives a treatment different than the randomized treatment for the duration of the placebo-controlled period, then that different treatment is the actual treatment; otherwise, the actual treatment is the planned treatment.

4.10.1. Extent of Exposure

Days of exposure will be calculated for each participant:

$$\text{date of last dose} - \text{date of first dose} + 1.$$

Summary statistics will be provided for the total number of days and participant-years of exposure by treatment. Study drug treatment assignment will be listed.

4.10.2. Adverse Events

Treatment-emergent adverse events (TEAEs) will be defined as events that occurred or worsened between the first dose (treatment start date) and two days post last dose (treatment end date), inclusive. Should there be insufficient data for AE start date, stop date, and time to make this

comparison, the AE will be considered treatment-emergent. The Medical Dictionary for Regulatory Activities (MedDRA) lower-level term (LLT) will be used in the treatment-emergent computation. The maximum severity for each LLT during the baseline period will be used as baseline.

An overview of AEs, including the number and percentage of participants who died, suffered serious adverse events (SAEs), discontinued due to AEs and who suffered TEAEs, will be provided. Comparison between treatments will be performed using Fisher's Exact Test.

Summaries of AEs by decreasing frequency of PT within SOC will be provided for the following:

- Pre-existing conditions
- TEAEs
- TEAEs by maximum severity
- TEAEs occurring in greater than or equal to 2% of participants by PT
- SAEs
- Adverse events reported as reason for study treatment discontinuation
- Adverse events of special interest (AESI) include, but not limited to, the following:

A black rectangular box containing the text 'CCI' in large, bold, red font.

These summaries will include number and percentages of participants with TEAEs. Treatment comparisons will be carried out using Fisher's Exact Test. A listing of AEs will be generated. Separated adverse events summaries will be provided for treatment period and follow-up period, respectively.

The following will be used to identify AESIs:

A black rectangular box containing the text 'CCI' in large, bold, red font.

The CCI logo is displayed in red text on a black rectangular background.

4.10.3. Deaths, Other Serious Adverse Events, and Other Notable Adverse Events

An overview of AEs, including the number and percentage of participants who died or suffered SAEs during the study, discontinued due to AEs and who suffered TEAEs, will be provided. Comparison between treatments will be performed using Fisher's Exact Test.

4.10.4. Clinical Laboratory Evaluation

Laboratory measurements will be analyzed using continuous data (change from baseline) and categorical or ordinal data (proportion of treatment-emergent abnormalities). If there are multiple records of laboratory measurements at baseline or postbaseline visit, the last record will be used. Summaries and analyses of continuous data (change from baseline) will be performed using both conventional and International System of Units (SI units) and include scheduled visits only. Listing will include data collected at unscheduled visits.

Measures of central tendency for laboratory measurements and change from baseline will be summarized with boxplots. Boxplots will display results quarterly for the first 24 weeks and semi-annually for the rest of the study period (Visit 5, 8, 15, 21, 25, 29, if applicable) and for the last visit (LOCF). Summary tables of N, mean, median, quartiles, min, max, standard deviation, and p-value (for change scores) will be included. If there are considerable missing visits, the measures of central tendency may be based on MMRM analyses.

Change from baseline to postbaseline visit at which laboratory measurements are taken will be compared between treatment groups using an MMRM model on the Safety Dataset. For each lab analyte, the rank-transformation will be applied to the change from baseline for all participants and all visits prior to analysis. Similarly, an independent rank-transformation will be applied to the baseline values prior to analysis. The model for the fixed effects will include the following terms: categorical effects of treatment, visit as a categorical variable, and treatment-by-visit interaction as well as the continuous effects of ranked baseline value and age at baseline. This analysis will be done separately for each laboratory analyte.

Treatment differences in the proportion of participants with treatment-emergent high or treatment-emergent low or treatment-emergent abnormal laboratory values at (1) anytime and (2) each postbaseline visit will be assessed using Fisher's Exact test. Treatment-emergent high or low laboratory abnormality will be based on SI unit. For each laboratory analyte, only participants who were low or normal at all baseline assessments and have at least 1 postbaseline will be included in the denominator when computing the proportion of participant with treatment-emergent high. Similarly, only participants who were high or normal at all baseline assessments and have at least 1 postbaseline will be included in the denominator when computing the proportion of participant with treatment-emergent low. In addition, treatment differences in the proportion of participants who have normal baselines with a change to abnormal high or abnormal low values at any postbaseline visits will be summarized.

For urinalysis parameters, baseline to postbaseline shifts will be summarized at each visit. Likelihood ratio chi-square tests will be used to compare increase, no change, and decrease shifts in urinalysis parameters between treatment groups at each visit.

For hormone panel parameters (i.e., follicle-stimulating hormone (FSH), luteinizing hormone (LH), Inhibin B, Testosterone, Estrogen), baseline to postbaseline values as well as change from baseline at each post-baseline visits will be summarized.

For all laboratory analytes, frequencies of participants with notable changes (i.e., increases or decreases of a pre-specified amount unique to each analyte) from baseline to each postbaseline visit were also summarized for all participants and stratified by low, normal, or high at baseline.

The proportion of subjects with treatment-emergent clinically significant changes from a low value or normal value at all baselines at any time in alanine aminotransferase (ALT), alkaline phosphatase (ALP), and total bilirubin will be summarized by treatment group. Clinically significant changes of interest for hepatic laboratory values at any time are: ALT or AST ≥ 3 x upper limit of normal (ULN), total bilirubin ≥ 2 x ULN, ALP ≥ 2 x ULN, ALT ≥ 5 x ULN, ALT ≥ 10 x ULN, and total bilirubin ≥ 2 x ULN. Additionally, Hy's Law analysis will be conducted by comparing treatment groups with regard to the proportion of participants with (ALT ≥ 3 x ULN OR AST ≥ 3 x ULN) AND total bilirubin ≥ 2 x ULN. Comparisons between treatment groups will be carried out using Fisher's Exact test. When criteria are met for hepatic evaluation and completion of the hepatic safety case report form (CRF), investigators are required to answer a list of questions pertaining to the participant's history, relevant preexisting medical conditions, and other possible causes of liver injury. A listing of the information collected on the hepatic safety CRF will be generated.

